5.4 Safety analyses

Safety data will be summarized and listed by treatment group for the SS, with the exception of AE listings which will be presented for the ASPS.

5.4.1 Extent of exposure

Exposure data will be listed for each study participant in the SS by treatment group. This listing will include date of first dose, date of last dose, total number of capsules taken, duration of exposure and overall IMP compliance (see [Section 6.1.8](#) for how this is calculated).

The duration of exposure to IMP (days) will be calculated as follows:

$$\text{Duration} = (\text{Date of Last Dose} - \text{Date of First Dose}) + 1 \text{ days}$$

Participants who have any dosing interruptions during the study (temporarily stop taking medication) will have multiple rows in this table. Therefore, a column for “cumulative duration” will also be presented. Participants who have a dosing interruption will be flagged.

Duration of exposure and total number of capsules taken will be summarized using descriptive statistics by treatment group based on the SS and will be presented in the same summary table as study medication compliance (see [Section 6.1.8](#)).

5.4.2 Adverse events

AEs will be collected from the time of signing the informed consent form (ICF) until the final SFU visit, and will be characterized as pre-treatment and treatment emergent according to intake of study medication. Adverse events with a start date prior to the first dose of treatment will be defined as pre-treatment AEs. A treatment-emergent AE (TEAE) is defined as any AE with a start date on or after the first dose of treatment or any unresolved event already present before administration of treatment that worsens in intensity following exposure to the treatment. Any AE with onset date later than the SFU visit will not be considered as treatment-emergent and therefore will not be included in the tabulations of TEAEs. Where dates are missing or partially missing, AEs will be assumed to be treatment-emergent, unless there is clear evidence to suggest otherwise. Missing or partially missing dates for AEs will be handled as described in [Section 5.1.1](#).

An overview of the occurrence and incidence of TEAEs will be provided by treatment group. The overview will present individual occurrences as well as number and percentage of participants experiencing any of the following:

- Any TEAE
- Any Serious TEAE
- Participant discontinuation due to TEAEs
- Any drug related TEAEs
- Any severe TEAEs
- Permanent withdrawal of study medication due to TEAEs
- All deaths (AEs leading to death)
- Deaths (TEAEs leading to death)

Summaries of the occurrence and incidence of SAEs and TEAEs will be provided by MedDRA® SOC, HLT, PT and treatment group (including a “UCB0599 Total” column which pools the high and low dose groups). These summaries will be provided for the following:

- Incidence of TEAEs
- Incidence of SAEs
- Incidence of serious TEAEs and serious TEAEs by relationship
- Incidence of fatal TEAEs and fatal TEAEs by relationship
- Incidence of TEAEs leading to discontinuation
- Incidence of non-serious TEAEs
- Incidence of TEAEs by maximum intensity
- Incidence of TEAEs by relationship and maximum relationship
- Incidence of non-serious TEAEs above reporting threshold of 5% of study participants

- Incidence of non-serious TEAEs above reporting threshold of 5% of study participants by relationship

Summary tables will contain counts of study participant, percentage of study participants in parentheses and the number of events where applicable. A participant who has multiple events in the same SOC, HLT and PT during a given treatment will be counted only once in the participant counts for that treatment, but all events will be included.

In summaries including relationship, the following relationships will be summarized: 'Not related' and 'Related'. Participants who experience the same event multiple times will be included in the most related category for tabulations by maximum relationship. Events with missing relationship will be considered as 'Related' for summary purposes but recorded as missing in the listings.

In summaries including intensity, the following intensity categories will be summarized: 'Mild', 'Moderate', 'Severe'. Participants who experience the same event multiple times will be included in the most severe category for tabulations by maximum intensity. Events with missing intensity will be considered as 'Severe' events for summary purposes but recorded as missing in the listings.

Adverse event summaries will be ordered by alphabetical SOC, alphabetical HLT and decreasing frequency of PT within SOC in the "UCB0599 Total" group.

The following listings of AEs will be presented based on the ASPS:

- All AEs
- All Serious AEs
- Discontinuation due to AEs
- AEs leading to death
- AEs related to the wearable sensor
- COVID-19 Infections

All listings will be presented by treatment group and study participant and will include the onset date and outcome date of the event, the event duration (derived), time to onset (derived), pattern of event, intensity, relationship to study medication, action taken and outcome. AEs that led to discontinuation, TEAEs, AESIs and SAEs will be flagged where applicable.

In addition to the above, the following summary tables will be produced for use in the study Plain Language Summary (and are not required for the CSR):

- Incidence of Drug-related TEAEs (Overview)
- Incidence of Drug-related TEAEs by Preferred Term
- Incidence of Serious Drug-related TEAEs by Preferred Term

5.4.2.1 Adverse events of special interest (AESI)

An AESI is any AE that a regulatory authority has mandated be reported on an expedited basis, regardless of the seriousness, expectedness, or relatedness of the AE to the administration of a UCB product/compound.

For UCB0599, the following events require immediate reporting (within 24 hours regardless of seriousness) to UCB:

- Potential Hy's Law, defined as ≥ 3 times upper limit of normal (ULN) alanine aminotransferase (ALT) or aspartate aminotransferase (AST) with coexisting ≥ 2 times ULN total bilirubin in the absence of ≥ 2 times ULN alkaline phosphatase (ALP), with no alternative explanation for the biochemical abnormality (ie, without waiting for any additional etiologic investigations to have been concluded). Follow up information should then be reported if an alternative etiology is identified during investigation and monitoring of the participant.
- Hypersensitivity reactions (such as rash, angioedema, or anaphylaxis).

These AESIs will be identified based on MedDRA algorithms, standardized MedDRA queries (SMQs), HLTs and PTs as provided in [Section 6.1.6](#) of this SAP. These events will also be identified by the investigator, the investigator flag will be used for flagging events in our listings and for presenting summary tables. Any discrepancies between these two sources will be investigated.

AESIs will be flagged in the AE listings, they will also be presented in a separate listing. A summary of the occurrence and incidence of treatment-emergent AESIs will be provided by MedDRA® SOC, HLT, PT, treatment group and country. This summary will also be repeated by relationship to study medication.

5.4.3 Additional safety assessments

5.4.3.1 Clinical safety laboratory assessments

Hematology, clinical chemistry, coagulation and urinalysis parameters will be assessed, see table 5.3 below for a full list of which parameters will be analyzed. Other screening and laboratory tests to be carried out are also covered in this table. The schedule of activities (protocol section 1.3) gives details on when these assessments are performed.

Hematology, clinical chemistry and coagulation laboratory results that were performed locally should be included in laboratory listings but not in summary tables and figures. Laboratory re-test results will be used in summary tables only if the original scheduled test result is not available, if the original result is available re-tests will be treated as unscheduled.

Table 5–3: Clinical laboratory assessments

Laboratory Assessments	Parameters					
Hematology	Platelet Count		RBC Indices: MCV MCH %Reticulocytes	WBC Count with Differential: Neutrophils ^b Lymphocytes ^b Monocytes Eosinophils ^b Basophils ^b		
	RBC Count ^b					
	Hemoglobin ^b					
	Hematocrit					
Clinical Chemistry	Blood Urea Nitrogen (BUN)	Potassium	Aspartate Aminotransferase (AST)/ Serum Glutamic-Oxaloacetic Transaminase (SGOT) ^b	Total and direct bilirubin		
	Creatinine	Sodium	Alanine Aminotransferase (ALT)/ Serum Glutamic-Pyruvic Transaminase (SGPT) ^b			
	Glucose (fasting at Screening and nonfasting at any visit thereafter)	Calcium	Alkaline phosphatase ^b			
Coagulation	International normalized ratio	Prothrombin time ^b	aPTT	Fibrinogen		
Routine Urinalysis	
 • Specific gravity • pH, glucose, protein, blood, ketones, bilirubin, urobilinogen, nitrite, leukocytes by dipstick • Microscopic examination (if blood or protein is abnormal) 					
Other Screening Tests	
 • Follicle-stimulating hormone and estradiol (as needed in women of non-childbearing potential only) • Immunoglobulin E • HbA1c (as needed in study participants with type 2 diabetes mellitus) • Urine drug screen (to include at minimum: amphetamines, barbiturates, cocaine, opiates, cannabinoids, methadone, and benzodiazepines) • Urine alcohol test • Serum and urine human chorionic gonadotropin (hCG) pregnancy test (as needed for women of childbearing potential)^a 					

Table 5–3: Clinical laboratory assessments

Laboratory Assessments	Parameters
	
• Serology (HIV antibody, hepatitis B surface antigen, and hepatitis C virus antibody) 
All study-required laboratory assessments will be performed by a central laboratory. The results of each test must be entered into the eCRF.

Other Laboratory Tests	
• RBC count and/or hemoglobin in CSF for quality control purposes

Note: Details of liver chemistry stopping criteria and required actions and follow-up assessments after liver stopping or monitoring event are given in Section 7.1.1 of the protocol and Appendix 6 of the protocol (Section 10.6). All events of ALT $\geq 3 \times$ upper limit of normal (ULN) and bilirubin ≥ 2 ULN ($>35\%$ direct bilirubin) or ALT $\geq 3 \times$ ULN and international normalized ratio (INR) >1.5 , if INR measured, may indicate severe liver injury (possible Hy's Law) and must be reported as an SAE.

^a Local urine testing will be standard for the protocol unless serum testing is required by local regulation or IRB.

^b Shift tables will be presented for these variables.

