## 2.3 Benefit/Risk assessment

To date, there are no approved 'neuroprotective' and/or 'disease-modifying' treatments to stop or slow disease progression of PD, which remains a large unmet medical need.

UCB0599 acts at an early-stage of ASYN aggregation by inhibiting the initial nucleation event or seed formation by inhibiting misfolding; therefore, it may halt the progression of PD vs only treating the symptoms. The outcome of this study will support the development of a medication that may provide a potential benefit for patients with PD.

Drug hypersensitivity is an important identified risk. Other potential risks include: hepatotoxicity (based on clinical data) and cardiac effects. Renal laboratory abnormalities are also kept under close safety monitoring.

In Phase 1 development of UCB0599, 5 studies (UP0030, TM0017, UP0023, UP0077, and UP0078) demonstrated that UCB0599 has acceptable safety, PK and tolerability profiles for further clinical development. Overall, the majority of treatment-emergent adverse events (TEAEs) were mild or moderate in intensity and resolved. In UP0030, 2 events of hypersensitivity were reported. An additional 2 events of hypersensitivity occurred in study participants who received UCB0599 in UP0077. A causal relationship between the reported events of drug hypersensitivity and UCB0599 is considered plausible. The hypersensitivity reactions are further described in the IB.

There have been no reports of anaphylaxis in the UCB0599 clinical program.

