5. Study participant is confirmed positive for recreational drug use or for alcohol at a Baseline Visit (Day 0), which is deemed significant enough to impair the study participant’s safety or the quality of the collected data. Outcome should be decided on a case-by-case basis.
6. Renal toxicity considered possibly related to the IMP. Laboratory tests suggestive of renal toxicity which should trigger further assessment may include:
  - Increase in serum creatinine  $\geq 0.3\text{mg/dL}$  OR
  - Increase in serum creatinine to  $\geq 1.5$  times from Baseline OR
  - New persistent albuminuria or clinically significant increase in pre-existing albuminuria, over 6 consecutive weeks

Any clinically significant findings in laboratory results for renal function will be monitored until resolution or stabilization.

7. The Sponsor requests withdrawal of the participant.
8. Study participant takes part in any other interventional study during the duration of this study.

Investigators should contact the Medical Monitor, whenever possible, to discuss the withdrawal of a participant in advance.

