#### **8.3.6.2 Renal function safety monitoring and management**

If a participant develops clinically significant renal dysfunction, repeat laboratory testing should be undertaken as soon as possible and other appropriate investigations may be arranged. An increase in serum creatinine of >25% from the previous value will trigger repeat testing within 48 hours. The Medical Monitor should be notified and consideration should be given to more frequent monitoring.

Clinically significant renal dysfunction will trigger an SMC and DMC review.

Participants must be discontinued from study medication (but not necessarily from the study) if laboratory tests suggest evidence of renal toxicity (see Section 7.2). Any clinically significant findings in laboratory results for renal function will be monitored until resolution or stabilization.

The SMC and DMC charters will include further details regarding the assessment of renal function.

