5.4.3.1.1 Laboratory values over time

Laboratory variables will be grouped according to the laboratory function panel and categorized as normal, high or low, if applicable, based on the reference range supplied by the analytical laboratory.

For urinalysis, hematology, coagulation and clinical chemistry observed results and changes from Baseline for numeric variables at each post-Baseline visit will be listed by treatment group, study participant and visit. Listings will flag values that fall outside of the normal range, and will include the reference ranges. Additionally, values that fall outside the reference ranges will be listed separately.

Clinical chemistry and hematology variables will be summarized descriptively by treatment group at each visit, for both observed values and changes from Baseline. These descriptive statistics will only be calculated if at most one third of the individual data points at any visit are missing or not quantifiable. If 3 or less participants have data available at any visit, only n, minimum and maximum will be presented. Plots of mean and mean change from Baseline will be presented by treatment group for all hematology and clinical chemistry laboratory variables. These plots will include all treatment groups overlaid on the same plot and will include error bars based on the SD (ie, mean \pm SD).

Measurements that are below the limit of quantification (BLQ) or above the limit of quantification (ALQ) will be presented as BLQ and ALQ in the listings. For the purpose of calculating change from Baseline or for descriptive statistics, BLQ values will be imputed with half of the lower limit of quantification (LLOQ) and ALQ values will be imputed to the upper quantification limit (if applicable).

A separate listing will be produced for study participants with Elevated Liver Function Results. Elevated results are defined as results meeting the following criteria:

- ALT or AST $\geq 3x$ (ULN)
- ALP $\geq 1.5x$ ULN
- Total bilirubin $\geq 1.5x$ ULN

The listing will display all scheduled and unscheduled visit data for participants who meet at least one of the above criteria was fulfilled. A summary of study participants who meet the criteria for potential drug-induced liver injury (PDILI) will be presented and a figure presenting liver function results over time for participants who meet the potential Hy's Law Criteria will be produced (this figure will only be produced if there are participants who meet the criteria).

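### Creatinine has no shift table, and no table counts participants by arm who reach the protocol's creatinine triggers, although renal laboratory abnormalities are under close monitoring

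*SAP*

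**What the plan says.** **Protocol.** Section 2.3 states: "Renal laboratory abnormalities are also kept under close safety monitoring". Section 7.2 lists reasons for which study medication must be stopped, and item 6 is: "Renal toxicity considered possibly related to the IMP". The same item continues: "Laboratory tests suggestive of renal toxicity which should trigger further assessment may include". It then gives three items: a creatinine rise of at least 0.3 mg/dL, a creatinine of at least 1.5 times Baseline, and "New persistent albuminuria or clinically significant increase in pre-existing albuminuria, over 6 consecutive weeks". Section 8.3.6.2 adds a repeat test within 48 hours when creatinine rises more than 25% from the previous value. It also says: "Clinically significant renal dysfunction will trigger an SMC and DMC review".

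**SAP, laboratory outputs.** Shift tables go only to variables carrying footnote b in Table 5-3: "Shift tables will be presented for these variables". Creatinine does not carry it. Under SAP 5.4.3.1.1, "Clinical chemistry and hematology variables will be summarized descriptively by treatment group at each visit, for both observed values and changes from Baseline". By SAP 5.1 those statistics are n, mean, SD, median, minimum and maximum. Mean plots, full listings with out-of-range flags, and a separate listing of out-of-range values are also planned.

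**SAP, what stays out of summary tables.** Section 5.1 keeps unscheduled data in listings unless stated otherwise. Section 5.4.3.1 keeps local chemistry results in listings, and uses a re-test only when the scheduled result is unavailable.

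**SAP, adverse events.** Section 5.4.2 counts TEAEs by treatment group. The events of special interest (5.4.2.1 and 6.1.6) are hypersensitivity and hepatic events; no renal grouping is planned.

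**The concern.** Safety and tolerability form the primary safety objective, and the kidney is one of the organ systems that the sponsor chose to watch. Drug-related renal injury usually shows as a sizeable rise in a few people. The natural output is therefore the number of participants in each arm whose creatinine crossed a stated limit. The protocol already supplies the limits, but the SAP does not turn them into a table.

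A rise that the investigator does not report as an adverse event could then be found only by reading listings, or inferred from the largest value at a visit. The clinical study report would contain no laboratory comparison of renal cases between arms that is independent of investigator reporting.

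**Working it through.** The plan states no figure on this point, so there is nothing to reproduce. The check traces where a creatinine rise would appear, and then illustrates how visible it would be.

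**1. Marked and unmarked variables (SAP Table 5-3).** Footnote b is on RBC count, hemoglobin, neutrophils, lymphocytes, eosinophils, basophils, AST, ALT, ALP and prothrombin time. It is not on creatinine, BUN or potassium. SAP 5.4.3.1.2 limits shift tables to the marked variables.

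**2. Where a rise could appear.**
- *By-visit summary:* a scheduled central-laboratory value enters the mean, SD, median and extremes. The maximum change shows that at least one participant rose that far at that visit. It does not show how many, or whether the same person supplies the maximum at successive visits.
- *Listings:* every value is there, flagged if out of range, but not counted.
- *Adverse event tables:* the rise is counted by arm if the investigator considers it clinically relevant and records it (Protocol 8.2.5).
- *Threshold table:* none for the kidney. For the liver, SAP 5.4.3.1.1 plans a listing of elevated results that includes unscheduled visits, a summary of potential drug-induced liver injury, an elevated-test summary table and several figures.

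**3. The repeat test.** The 48-hour repeat in Protocol 8.3.6.2 follows a scheduled result that already exists. Under SAP 5.4.3.1 it is then treated as unscheduled and is listed only. If the peak is seen at the repeat, it is missing even from the by-visit maximum.

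**4. How far cases move a mean.** The arm size is 150 (Protocol 9.7.1). Suppose k participants each rise by the trigger of 0.3 mg/dL, all at the same visit with all 150 measured. The shift in the arm mean is k × 0.3 / 150:
- k = 1 (0.7%): 0.002 mg/dL
- k = 3 (2.0%): 0.006 mg/dL
- k = 5 (3.3%): 0.010 mg/dL
- k = 8 (5.3%): 0.016 mg/dL

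These are the largest shifts for these k at that rise; rises spread over visits move each visit's mean less.

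**5. Whether such cases would occur.** The documents give no rate, so rates are assumed. For X binomial with n = 150, P(X ≥ 3) = 1 − P(0) − P(1) − P(2):
- rate 1%: 0.19
- rate 2%: 0.58
- rate 3%: 0.83
- rate 5%: 0.98

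At 2% or more, a handful of cases in an arm is more likely than not.

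**6. Why a shift table alone is not enough.** It classifies values as below, within or above the normal range. A rise of 0.3 mg/dL may stay within range. Exclusion 40b admits participants with eGFR down to 45 mL/min/1.73m², so some may start above range and stay in the same cell after a rise. Only a count against the triggers catches both.

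**7. How the two creatinine triggers relate.** A value of 1.5 times Baseline b is a rise of 0.5 × b. This is below 0.3 mg/dL only if b < 0.6 mg/dL. For b of 0.6 or more, everyone who meets the ratio trigger also meets the absolute one, so the two should be shown as separate rows.

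**The case against.** The best defence is that the renal picture is better covered than the absence of a shift table suggests, and much of that defence stands.

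- A reader might infer that creatinine is reported only as means. It is not: SD, median, minimum and maximum of values and changes are given by arm and visit.
- A reader might infer that renal cases would appear in no count by arm. That is also wrong. Clinically relevant laboratory changes must be recorded as adverse events, and TEAEs, TEAEs leading to discontinuation and permanent drug withdrawals due to TEAEs are counted by treatment group. A stop under item 6 would normally appear there.
- The creatinine values in 7.2 are not themselves the stopping criterion. They prompt assessment, the list is open-ended, and the criterion is toxicity possibly related to the drug. Section 8.3.6.2 is worded more directly ("Participants must be discontinued from study medication (but not necessarily from the study) if laboratory tests suggest evidence of renal toxicity") but refers back to 7.2. A count of triggers is therefore not a count of renal toxicity.
- The liver is not an exact comparator: hepatotoxicity is listed as a potential risk and potential Hy's Law is an event of special interest, while renal findings are neither.
- Renal oversight during the trial runs through the SMC and DMC, whose charters are not among these documents.

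These routes still leave a gap. The adverse event route depends on the investigator's view of clinical relevance and has no planned grouping of renal terms. A by-visit maximum is one value, not a number of people. Liver findings have the same adverse event route, and the sponsor still planned threshold outputs for them.

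**Conclusion.** The concern holds in a limited form. The SAP as written gives no shift table for creatinine and no by-arm count of participants reaching the protocol's own creatinine triggers. Cases not reported as adverse events would be visible only in listings and as by-visit extremes, with re-test, unscheduled and local results generally outside the summary tables.

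It is a modest reporting gap. It touches no estimand, power figure or participant protection. The illustration shows why it is worth closing: 3 to 8 cases in 150 would read as 2.0% to 5.3% in a count, against a mean shift of at most 0.006 to 0.016 mg/dL. The case numbers, the uniform 0.3 mg/dL rise and the rates are assumptions; only the trigger and the arm size come from the documents.

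Three further inferences are not supported. Cystatin C is missing from SAP Table 5-3 as it reads here, but so are the other items in the same column of the protocol's laboratory table. That fits cells lost in PDF reading, so it does not show that cystatin C is unanalysed. The eGFR limit of 45 is an entry limit, not an on-treatment criterion, and crossing it should not be presented as one. A significance test on an assumed split of cases between arms would prove nothing, since the documents give neither case rates nor the variability of creatinine change.

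**What to change.** In SAP 5.4.3.1:

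1. Add footnote b to creatinine in Table 5-3, so that it gets a shift table.
2. Add one table by treatment group with the number and percentage of participants who, at any post-Baseline time, reach the existing creatinine triggers of Protocol 7.2 item 6. Use separate rows for a rise of at least 0.3 mg/dL and for at least 1.5 times Baseline. State explicitly that unscheduled and re-test values are included, because SAP 5.1 and 5.4.3.1 would otherwise exclude them, and say whether local results count. Label the rows as triggers for assessment, not as confirmed renal toxicity.

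The albuminuria trigger is left out of this count because it needs persistence over time and a view on clinical significance. Summaries of dipstick protein by arm, and shift tables for BUN and potassium, are optional.

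The cost is SAP wording and a little programming on data already collected. The count will include some transient fluctuations, which is why the label matters. No clinical rule changes.
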